2.1 Sample size calculation

The primary objective of this trial is to confirm efficacy of IDegAsp BID ± metformin in terms of glycaemic control.

This is done by showing that:

IDegAsp BID ± metformin is non-inferior to BIAsp 30 BID ± metformin in terms of glucose lowering effect as assessed by change from baseline in HbA_{1c} after 26 weeks of treatment using a non-inferiority margin of 0.4% (absolute). Sample size is determined based on this primary objective.

Throughout this section of the protocol the term “investigational product” will be used as a synonym for IDegAsp BID and the term “comparator” will be used as a synonym for BIAsp 30 BID.

The non-inferiority margin of 0.4% (absolute) was chosen in accordance with the FDA guidance². Let D be the mean treatment difference for change in HbA_{1c} (investigational product minus comparator). The null-hypothesis will be tested against the alternative hypothesis of non-inferiority as given by

$$H_0: D > 0.4\% \quad \text{against} \quad H_A: D \leq 0.4\%$$

Operationally the null-hypothesis will be rejected and non-inferiority considered confirmed if the upper bound of the two-sided 95% confidence interval for the mean HbA_{1c} treatment difference is below or equal to 0.4%. This is equivalent to using a one-sided test of size 2.5%.

Sample size is determined using a t-statistic under the assumption of a one-sided test of size 2.5% and a zero mean treatment difference (i.e. D=0%). Based on experience from previous phase 3 trials in subjects with type 2 diabetes treated with insulin an estimate for the standard deviation (SD) of 1.3% for HbA_{1c} will be used in the sample size calculation ([Table 2-1](#)). The sample size calculation is done using SAS 9.3.

Table 2–1 Specifications assumed for sample size calculation

Statistical test	One sided Significance Level	Non- inferiority Margin	SD	Mean Difference	Randomisati on Scheme	Required Power
two-group t test	2.5%	0.4% (absolute)	1.3%	0.0%	2:1	87%

Table 2–2 Sensitivity of sample size (integers) to variations in SD and power

#subjects in total	SD=1.1	SD=1.2	SD=1.3	SD=1.4
Power = 80%	270	321	375	435
Power = 85%	309	366	429	498
Power = 87%	327	390	456	528
Power = 90%	360	429	504	582

From [Table 2–2](#) it is seen that the primary objective will be met with at least 87% power with 456 subjects assuming a SD of 1.3%.

As this is a non-inferiority trial sample size will be determined such that the anticipated power is at least 87% in the evaluation of the PP analysis set. In previous phase 3 trials in type 2 diabetes treated with insulin 5-25% of the randomised subjects were excluded from the PP analysis set. The number of excluded subjects was dependent on the trial design. In this trial an estimate of 15% will be used and sample size is ceiled in the FAS to have integer sample size for each group that adheres exactly to the group allocation weights (2:1). Hence the total number of subject to be randomised must be 537 subjects in order to have at least 87% power in the evaluation of the PP analysis set (**Error! Reference source not found.**).

Table 2–3 Anticipated number of subjects in FAS and PP analysis set

	IDegAsp BID	BIAsp 30 BID	Total
Number of subjects in the FAS	358	179	537
Number of subjects in the PP	304	152	456

Definition of analysis sets

2.2 Definition of analysis sets

- Full Analysis Set (FAS): includes all randomised subjects. In exceptional cases subjects from the FAS may be eliminated. In such cases the elimination will be justified and documented. The statistical evaluation of the FAS will follow the intention-to-treat (ITT) principle and subjects will contribute to the evaluation “as randomised”.
- The Per-Protocol analysis set will consist of all subjects in the Full Analysis Set who fulfils the following criteria:
 - Have not violated any inclusion criteria
 - Have not fulfilled any exclusion criteria
 - Have a non-missing HbA_{1c} at screening or randomisation
 - Have at least one non-missing HbA_{1c} after 12 weeks of exposure
 - Have at least 12 weeks of exposure

Subjects will contribute to the evaluation “as treated”.

Safety Analysis Set: includes all subjects receiving at least one dose of the investigational product or its comparator. Subjects in the safety set will contribute to the evaluation “as treated”.

Randomised subjects who are lost to follow up and where no exposure information of the investigational product or its comparator is available after randomisation will be handled as unexposed. The OADs that the subjects are included on and will stay on throughout the trial are concomitant medications and regarded as non-investigational products.

Before data are released for statistical analysis, a review of all data will take place to ensure a sufficient data quality and to ensure the planned statistical analyses are applicable. Any data decisions e.g. classification of anti-diabetic treatment not foreseen in the protocol, will be documented before database lock.

2.3 Primary endpoint

The primary endpoint is change from baseline in HbA_{1c} (%) after 26 weeks of treatment

2.3.1 Statistical analysis

Change from baseline in HbA_{1c} after 26 weeks of treatments will be analysed using an Analysis of Variance (ANOVA) method with treatment, anti-diabetic therapy at screening and sex as fixed factors, and age and baseline HbA_{1c} as covariates. The anti-diabetic therapy at screening is a factor with the following four levels:

- Basal insulin regimen without metformin
- Basal insulin regimen with metformin
- Premix/self-mix regimen without metformin

- Premix/self-mix regimen with metformin

The model will be fitted using FAS and from this model the relevant treatment differences will be estimated.

Non-inferiority will be considered confirmed if the upper bound of the two-sided 95% confidence interval is below or equal to 0.4% or equivalent if the p-value for the one-sided test of

$H_0: D > 0.4\%$ against $H_A: D \leq 0.4\%$,

is less than or equal to 2.5%, where D is the mean treatment difference (investigational product minus comparator)

If non-inferiority is confirmed the superiority of the investigational product over comparator in change from baseline HbA_{1c} (%) after 26 weeks of treatment will be investigated. Superiority will be considered confirmed if the upper bound of the two-sided 95% confidence interval, which is calculated using the FAS, is below 0%. The PP analysis is considered supportive here.

The HbA_{1c} analyses will be carried out in both standard unit (%) and converted unit (mmol/mol), but the results given in % are considered confirmatory. Subjects with HbA_{1c} < 4.1 % (i.e. LLOQ) will get a converted value of LLOQ/2=10.6565 mmol/mol instead of the negative value that would have resulted from using the standard formula $10.93 * \text{value}(\%) - 23.5$.

2.3.2 Sensitivity analysis

The primary efficacy analysis will be repeated on the PP analysis set and the set of all completed subjects as sensitivity analyses.

The following sensitivity analyses will be performed using the FAS only.

All observed HbA_{1c} measurements available post randomisation at scheduled measurement times will also be analysed in a linear mixed model using an unstructured residual covariance matrix (if possible), and with treatment, time, interaction between treatment and time, anti-diabetic treatment at screening and sex as fixed effects and age and baseline HbA_{1c} as covariates.

This approach relies on the assumption that data are missing at random (MAR) according to the taxonomy defined by Rubin.³ The results will be compared to the results of the LOCF method for dealing with missing data. Any marked difference concerning treatment differences between the MAR and LOCF approach will be commented upon in the CTR.

Change in HbA_{1c} from baseline will also be analysed using a model with only treatment as fixed factor and baseline HbA_{1c} as covariate to assess the sensitivity of the results to inclusion/exclusion of fixed factors and covariates.

2.4 Secondary endpoints

2.4.1 Confirmatory secondary endpoints

Provided that non-inferiority is confirmed for the primary endpoint, a number of confirmatory secondary endpoints will be tested to confirm superiority of the investigational product over the comparator.

The confirmatory secondary endpoints are given below together with the direction of the test for superiority. The order of the endpoints defines the testing sequence.

1. Change from baseline in FPG after 26 weeks of treatment (analysed at central laboratory)
 - Superiority is considered confirmed if the 95% confidence interval for the treatment difference (investigational product minus comparator) is entirely below zero
2. Number of treatment emergent nocturnal confirmed hypoglycaemic episodes
 - Superiority is considered confirmed if the 95% confidence interval for the relative risk (investigational product / comparator) is entirely below one
3. Number of treatment emergent confirmed hypoglycaemic episodes
 - Superiority is considered confirmed if the 95% confidence interval for the relative risk (investigational product / comparator) is entirely below one
4. Change from baseline in body weight after 26 weeks of treatment
 - Superiority is considered confirmed if the 95% confidence interval for the treatment difference (investigational product minus comparator) is entirely below zero
5. Responder without hypoglycaemic episodes (HbA_{1c} <7.0% after 26 weeks of treatment and no confirmed episodes during the last 12 weeks of treatment or within 7 days after the last randomised treatment including only subjects exposed for at least 12 weeks)
 - Superiority is considered confirmed if the 95% confidence interval for the odds ratio (investigational product / comparator) is entirely above one

Change from baseline in FPG

Change from baseline in FPG after 26 weeks of treatment will be analysed using an ANOVA method with treatment, anti-diabetic therapy at screening and sex as fixed factors, and age and baseline FPG as covariates.

Number of treatment emergent confirmed hypoglycaemic episodes

A hypoglycaemic episode is defined as treatment emergent if the onset of the episode is on or after the first day of exposure to randomised treatment and no later than 7 days after the last day of randomised treatment.

The number of confirmed hypoglycaemic episodes will be analysed using a negative binomial regression model with a log-link function and the logarithm of the time period in which a hypoglycaemic episode is considered treatment emergent as offset. The model will include treatment, anti-diabetic therapy at screening and sex as fixed factors, and age as covariate.

Number of treatment emergent nocturnal confirmed hypoglycaemic episodes

A hypoglycaemic episode that has time of onset between 00:01 and 05:59 a.m. (both included) will be considered nocturnal.

The number of treatment emergent nocturnal confirmed hypoglycaemic episodes will be analysed using a negative binomial regression model with a log-link function and the logarithm of the time period in which a hypoglycaemic episode is considered treatment emergent as offset. The model will include treatment, anti-diabetic therapy at screening and sex as fixed factors and age as covariate.

Change from baseline in body weight

Body weight is assessed at trial site. Change from baseline in body weight after 26 weeks of treatment will be analysed using an ANOVA method with treatment, anti-diabetic therapy at screening and sex as fixed factors, and age and baseline body weight as covariates.

Responder without hypoglycaemic episodes

Responder without hypoglycaemic episodes is a dichotomous endpoint (responder/non-responder) that is defined based on whether a subject has met the ADA HbA_{1c} target (< 7%) after 26 weeks of treatment without treatment emergent confirmed hypoglycaemic episodes during the last 12 weeks of treatment or within 7 days after last randomised treatment. The endpoint will only be defined for subjects that have been exposed to the investigational product or its comparator for at least 12 weeks.

Responder analysis will be based on a logistic regression model using treatment, anti-diabetic therapy at screening and sex as fixed factors, and age and baseline HbA_{1c} as covariates.

2.4.2 Supportive secondary endpoints

2.4.2.1 Efficacy

The timing of assessments is outlined in the trial flow chart.

HbA_{1c} responder endpoints

Two dichotomous endpoints (responder/non-responder) will be defined based on whether a subject has met the ADA HbA_{1c} target (HbA_{1c} < 7.0%) and the International Diabetes Federation (IDF) HbA_{1c} target (HbA_{1c} ≤ 6.5%) after 26 weeks of treatment.

Additional dichotomous endpoints will be defined based on whether those treatment targets after 26 weeks of treatment are achieved without hypoglycaemic episodes in the last 12 weeks of treatment or within 7 days after last randomised treatment considering confirmed episodes and severe episodes only. These endpoints will only be defined for subjects that have been exposed for at least 12 weeks.

The responder endpoints will be analysed separately based on a logistic regression model using treatment, anti-diabetic therapy at screening and sex as fixed factors, and age and baseline HbA_{1c} as covariates.

Self measured plasma glucose

Self-measured plasma glucose will be measured in terms of the 9-point profiles (SMPG) and glucose measurements used for insulin dose adjustments.

9-point profile (SMPG) after 26 weeks of treatment

A 9-point profile (SMPG) will include measurements before and 90 minutes after start of breakfast, lunch and main evening meal, measurements prior to bedtime and at 4 a.m., and one before breakfast the following day.

The endpoints from the 9-point profiles (SMPG) will be:

- 9-point profile (SMPG)
- Mean of the 9-point profile (SMPG)
- Fluctuation in the 9-point profile (SMPG)
- Prandial plasma glucose (PG) increments

The mean of 9-point profile (SMPG) is defined as the area under the profile divided by the measurement time and is calculated using the trapezoidal method. The fluctuation in the 9-point profile (SMPG) is defined as

$$\frac{1}{T} \int_0^T |PG(t) - \overline{PG}| dt$$

where T , $PG(t)$ and \overline{PG} denotes the length of the profile, the PG value at time t and the mean of the profile, respectively.

Prandial PG increment for each meal will be derived from the 9-point profile (SMPG) as the difference between PG values available 90 minutes after meal and before meal. Mean prandial PG increment over all meals will be derived as the mean of all available meal increments.

A mixed effect model will be fitted to the 9-point profile (SMPG) data. The model will include treatment, time, interaction between treatment and time, anti-diabetic therapy at screening and sex as fixed factors, age and the values from the profile at baseline as covariates and subject as random effect. From the model, mean profile by treatment and relevant treatment differences will be estimated and explored.

Mean and fluctuation in the 9-point profile (SMPG) and prandial PG increment endpoints will be analysed separately using an ANOVA method with treatment, anti-diabetic therapy at screening and sex as fixed factors, and age and the relevant baseline value as covariates. Fluctuation in the 9-point profile (SMPG) will be logarithm transformed before analysed.

2-point profile (SMPG) values used for dose adjustment

The endpoints from the SMPG measurements obtained throughout the trial for dose adjustment will be:

- Mean PG before meals (breakfast and main evening meal) after 26 weeks of treatment
- Responder for PG titration targets
- Time from randomisation (measured in weeks) to achieve titration targets
- Within-subject variability as measured by CV% after 26 weeks of treatment

The mean PG value before a meal will be calculated at each visit using the available data and separately for breakfast and main evening meal.

The mean before meal PG values after 26 weeks of treatment will be analysed separately, using an ANOVA method with treatment, anti-diabetic therapy at screening and sex as fixed factors, and age as covariates.

From the mean before meal PG value, a dichotomous endpoint (responder/non-responder) will be derived for each meal that shows if a subject has achieved the titration target at each visit.

For each target a survival endpoint will be derived as the time from randomisation to the date a subject achieves the titration target for the first time.

The two survival endpoints will be analysed separately in a Cox proportional hazards model including treatment, anti-diabetic therapy at screening and sex as fixed factors and age as covariate. An analysis will also be performed for the time to all titration targets are met. Subjects that are lost

for follow up without meeting the target and subjects that never meet the target during treatment will be censored at the last day of treatment.

The logarithm transformed SMPG values available before breakfast and main evening meal, will be analysed separately as repeated measures in a linear mixed model with treatment, anti-diabetic therapy at screening and sex as fixed factors, age as covariate and subject as random factor. The model will assume independent within- and between-subject errors with variances depending on treatment. Within-subject variability as measured by CV% for a treatment can be calculated from the corresponding residual variance σ^2 as $CV\% = 100\sqrt{(\exp(\sigma^2)-1)}$. The confidence interval for the CV ratio between treatments will be calculated using the delta method.

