#### 4.2.3 Supportive secondary endpoints

##### 4.2.3.1 Efficacy

Supportive secondary endpoints will be described in detail in section [17](#) of this protocol, and are therefore only listed below without detailed explanation. The timing of assessments is outlined in the trial flow chart.

- Responder for  $HbA_{1c}$  after 26 weeks of treatment
  - $HbA_{1c} < 7\%$
  - $HbA_{1c} \leq 6.5\%$
  - $HbA_{1c} < 7\%$  without severe hypoglycaemic episodes during the last 12 weeks of treatment or within 7 days after the last randomised treatment including only subjects exposed for at least 12 weeks
  - $HbA_{1c} \leq 6.5\%$  without confirmed hypoglycaemic episodes during the last 12 weeks of treatment or within 7 days after the last randomised treatment including only subjects exposed for at least 12 weeks
  - $HbA_{1c} \leq 6.5\%$  without severe hypoglycaemic episodes during the last 12 weeks of treatment or within 7 days after the last randomised treatment including only subjects exposed for at least 12 weeks
- 9-point profile (SMPG) after 26 weeks of treatment
  - 9-point profile (SMPG)
  - Mean of the 9-point profile (SMPG)
  - Fluctuation in the 9-point profile (SMPG)
  - Prandial plasma glucose (PG) increment
- 2-point profile (SMPG) measurements obtained throughout the trial for dose adjustment
  - Mean PG before meals after 26 weeks of treatment
  - Responder for PG titration targets
  - Time from randomisation (measured in weeks) to achieve titration targets

- Within-subject variability as measured by coefficient of variance (CV)% after 26 weeks of treatment

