#### 8.6.9.1 2-point profile (SMPG)

Subjects will be asked to perform SMPG measurements before breakfast and before main evening meal. Pre-breakfast measurements should preferably be performed on the day of the dose adjustment and the two consecutive days just before Visit 3-28. Pre-main evening meal measurements should preferably be performed three consecutive days just before Visit 3-28. The measurements should be performed using the glucose meter provided. SMPG measurements before breakfast should preferably be performed after having consumed only water since midnight. These measurements are required for optimal insulin dose adjustment and maintenance as described in the titration guideline (Appendix A).

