In addition, if non-inferiority can be confirmed and the 95% confidence interval for the mean HbA_{1c} treatment difference not only lies entirely below 0.4% but also below zero this will be considered as evidence of superiority of the investigational product over the comparator in terms of change from baseline in HbA_{1c} after 26 weeks of treatment.

Only endpoints derived after 26 weeks of treatment will be analysed statistically. Missing values will be imputed using the Last Observation Carried Forward (LOCF) method. LOCF has been a standard approach in diabetes trials for many years, and was used as the primary analysis in all degludec phase 3a trials. LOCF is considered to be an appropriate method in the context of treat-to-target trials, where subjects after withdrawal typically continue their therapy using commercially available insulin. In previous treat-to-target trials with degludec LOCF has generally provided similar results to alternative methods to handle missing data, such as repeated measures models and completer analyses. In this trial, similar sensitivity analyses will be made to examine the robustness of the LOCF method. All endpoints will be summarised descriptively at each visit by treatment and in total using observed data. After 26 weeks of treatment, descriptive statistics will be presented based both on observed and Last Observed Value (LOV) data, which corresponds to LOCF imputed data. Endpoints that are analysed untransformed and endpoints that are not formally analysed are summarised by the arithmetic mean, standard deviation (SD), median, and minimum and maximum value. Endpoints that are analysed log-transformed are summarised by the geometric mean, CV, median, minimum and maximum value.

LOCF imputed data will be used as the basis for plotting data if not otherwise specified.

Presentation of results from a statistical analysis will include the estimated mean treatment effects (least-squares means [LSMeans]) for absolute values and change from baseline if applicable. Estimated mean treatment differences (or ratios) will be presented together with two-sided 95% confidence intervals for all endpoints analysed statistically. P-values will only be presented for the primary and the confirmatory secondary endpoints for which formal statistical testing will be performed. The other endpoints are considered supportive and explorative in nature and no p-values will be presented.

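### The interval for the within-subject CV ratio assumes one day-to-day variance per arm, and is too narrow if subjects differ in variability

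*SAP*

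**What the plan says.** Protocol 4.2.3.1 lists among the supportive efficacy endpoints "Within-subject variability as measured by coefficient of variance (CV)% after 26 weeks of treatment", and SAP 2.4.2.1 repeats it. The data are the 2-point profile readings before breakfast and before the main evening meal, analysed separately for each meal on the log scale. The model has treatment, therapy at screening and sex as factors, age as covariate and subject as random factor. On the variances, the SAP says: "The model will assume independent within- and between-subject errors with variances depending on treatment". CV% for each arm follows from that arm's residual variance. For the comparison, "The confidence interval for the CV ratio between treatments will be calculated using the delta method". Protocol 17.4.2.1 has the same text.

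SAP section 2 (Statistical considerations) asks for two-sided 95% intervals for everything analysed statistically. It also gives the endpoint's standing: "The other endpoints are considered supportive and explorative in nature and no p-values will be presented". Neither document names a robust variance, a bootstrap or a sensitivity analysis for the CV ratio.

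**The concern.** The quantity being compared is itself a variance. The standard error of an estimated variance depends on the fourth moment of the data, so it is sensitive to assumptions that hardly matter when means are compared. The delta method only carries forward the variance it is given. With nothing else specified, that is presumably the model-based one, which assumes normal residuals and the same variance for every subject in an arm.

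If subjects differ in day-to-day variability, the subject-level variances scatter more than the model allows. The pooled estimate is then less precise than its stated standard error. More subjects do not cure this, because the true and the model-based standard errors shrink at the same rate. At stake is an interval that excludes 1 too often when the two insulins give equal variability. No p-value is planned, so the interval is the only inferential result for this comparison, and it is produced twice, once for each meal.

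**Working it through.** **Inputs from the documents.** The plan gives no figure for the CV ratio or its interval. The arm sizes come from SAP Table 2–3 and reproduce: 152/0.85 = 178.8, rounded up to 179; 2 × 179 = 358; total 537. The noncentral-t power for 456 subjects is 87.1%, as planned. The number of readings per subject and meal at week 26 is k = 3. For breakfast, protocol 8.6.9.1 says "Pre-breakfast measurements should preferably be performed on the day of the dose adjustment and the two consecutive days just before Visit 3-28"; for the evening meal it asks for three consecutive days before the visit.

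**Assumptions.** Let v be a subject's true variance of log glucose, with mean σ² and squared coefficient of variation c across subjects. The documents give no value for c, so a range is shown. Take σ² = 0.04, which is a CV of 100√(exp(0.04) − 1) = 20.2%. Data are complete, there is no serial correlation, and the true CV ratio is 1.

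**Variance of one subject's sample variance.**

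- Under the model: 2σ⁴/(k − 1), which is σ⁴ for k = 3.
- With unequal variances: 2σ⁴(1 + c)/(k − 1) + cσ⁴, which is σ⁴(1 + 2c) for k = 3.
- True SE over model SE is therefore √(1 + 2c), whatever the number of subjects. For general k it is √(1 + c(k + 1)/2).

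**Model-based SE of the log CV ratio.** The derivative of log CV with respect to σ² is exp(σ²)/[2(exp(σ²) − 1)] = 12.75. The SE is 12.75 × √(0.04²/358 + 0.04²/179) = 0.0467. The planned interval is then the estimate divided and multiplied by exp(1.96 × 0.0467) = 1.096.

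**Effect of unequal variances.** Expected coverage is 2Φ(1.96/SE ratio) − 1. The factor is exp(1.96 × 0.0467 × SE ratio).

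| c | SE ratio | Planned interval too narrow by (log scale) | Coverage, formula | Coverage, simulated | Factor for a correct interval |
|---|---|---|---|---|---|
| 0 | 1.00 | 0% | 95.0% | 95.1% | 1.096 |
| 0.0625 | 1.06 | 6% | 93.5% | 93.7% | 1.102 |
| 0.25 | 1.22 | 18% | 89.0% | 89.3% | 1.119 |
| 0.5 | 1.41 | 29% | 83.4% | 83.6% | 1.138 |
| 1 | 1.73 | 42% | 74.2% | 74.6% | 1.172 |

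**What c means.** If subject variances are lognormal, the middle 95% of subjects span a range in day-to-day SD of exp(1.96√ln(1 + c)). That is 1.6-fold at c = 0.0625, 2.5-fold at 0.25, 3.5-fold at 0.5 and 5.1-fold at 1.

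**Heavy tails.** With equal subject variances but t-distributed residuals, simulated coverage was about 80% on 5 degrees of freedom and 90% on 8.

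**After the change.** Taking the variance from the spread of the subject-level variances, and passing it through the same delta method, gave about 94–95% coverage at every c from 0 to 1. A bootstrap of whole subjects gave 92–95%.

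**The case against.** The mechanism is not in dispute; its size is. The documents give no measure of how far variability differs between subjects, and the log scale already removes variance that merely scales with glucose level. At c = 0.0625 the loss is about 1.5 points of coverage, which is negligible. At c = 0.25 the false-difference rate is about 11%, roughly twice nominal. The heavy-tail figures rest on a further assumption, and SAP section 2 leaves room for outlier sensitivity analyses, though these are optional and would not change the interval. All of this stands, and it rules out calling the interval much too narrow as a matter of fact.

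A reader might infer something far worse. The list of endpoints opens with "The endpoints from the SMPG measurements obtained throughout the trial for dose adjustment will be", and the model sentence does not say which visits it uses. If about 3 × 26 = 78 readings per subject were pooled, the SE ratio would be √(1 + 39.5c), and coverage would fall to about 45% at c = 0.25 and 24% at c = 1. The documents do not favour that reading. The endpoint is "Within-subject variability as measured by CV% after 26 weeks of treatment", and SAP section 2 states "Only endpoints derived after 26 weeks of treatment will be analysed statistically". Pooling the whole trial would also put the titration-driven fall in glucose into the residual of a model with no time term, which is a separate problem that this calculation does not represent. Those figures should not drive the severity.

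The delta method is also not at fault in itself. Given a subject-level variance, it performs well. Finally, the endpoint is supportive, lies outside the testing hierarchy and has no decision rule. The CV% of each arm is available beside the ratio.

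**Conclusion.** The concern holds in conditional form. As written, the interval is valid only under one normal residual variance per arm. If variability differs between subjects it is too narrow: by about 6% at c = 0.0625, 18% at c = 0.25 and 42% at c = 1. Equal arms would then be reported as different in about 6%, 11% and 25% of trials, against 5% nominal. These figures assume three complete readings per subject and meal and 358 and 179 subjects; c is not known.

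It does not follow that the trial's conclusions are at risk. The arm-level CV% and the point estimate of the ratio are unaffected, and so are the HbA1c result and the five confirmatory endpoints. Because exact equality of subject variances is a strong assumption and the remedy is cheap, the change is worth making, with a priority suited to a supportive endpoint.

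**What to change.** Keep the mixed model for the point estimate and make two changes in SAP 2.4.2.1.

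- State that only the readings taken for Visit 28, up to three per meal, enter the model.
- Base the 95% interval for the log CV ratio on a subject-level variance. This can be a subject-clustered (robust) variance carried through the delta method, or a bootstrap that resamples whole subjects within arm, for example 2000 times. Name one of them in advance.

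The cost is a sentence or two in the SAP and a few lines of code. If subject variances are in fact equal, the interval hardly changes: simulated coverage at c = 0 was 94.8–95.0% with the subject-level variance. If they differ, the interval widens, for example from a factor of 1.096 to about 1.12 either side of the estimate at c = 0.25. A departure from the protocol text should be listed in SAP section 3 with the other changes.
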